5.5 Justification for Dose

The current study design in Part A allows for a measured and stepwise exploration of doses, with the maximum dose for each participant limited by a normalization of cardiac contractility or resolution of clinical parameters of LVOT obstruction.

In a previous study with a similar compound (mavacamten), the exposure-response relationship for LVEF varied between healthy volunteers (HV) and HCM patients, with a higher baseline LVEF and a steeper slope for HCM patients. These observations are likely a manifestation of the underlying pathobiology of sarcomeric hypercontractility that is a hallmark of the disease. We anticipate a similar phenomenon with MYK-224 and have thus chosen a starting dose and an echocardiography-based dose titration scheme that will allow for safe and stepwise dose modification guided by each participant's response parameters.

[REDACTED]. Additionally, given that HCM patients may exhibit relief of LVOT obstruction at lower exposures than at which effects on LVEF are observed, participants that demonstrate a clinical response at [REDACTED]

The starting dose of MYK-224 in the current study will be 5 mg, which has been shown to be safe and well-tolerated in the FIH study in normal healthy participants.

[REDACTED]

[REDACTED]

Participants will resume dosing in Part B at the dose they had completed Part A. This serves as a reasonable starting point for further dosing since this is a dose that was selected according to each participant's echocardiographic response to the study drug and was a dose that was tolerated to study completion. In cases where background therapy was modified between study parts, participants will either resume previous therapy prior to screening and start at the dose they completed in Part A or start at a 5-mg dose (see [Section 7.4](#) for details on starting dose for Part B). This will allow a safe starting point for subsequent dose titration to identify a new dose in the context of altered background therapy.

[REDACTED] (see [Section 7.4](#) [Dose Modification]). The dose of MYK-224 may be decreased at any time during the study based on

the clinical judgement of the investigator in discussion with the Medical Monitor. [REDACTED]
[REDACTED] (see [Section 8.1](#)).

6 STUDY POPULATION

Prospective approval of protocol deviations to recruitment and enrollment criteria, also known as protocol waivers or exemptions, is not permitted.

6.1 Inclusion Criteria

This study will include both male and female participants, including women of childbearing potential (WOCBP). Participants are eligible to be included in the study only if all of the following criteria apply:

PART A:

1) Signed Written Informed Consent

Participants must have signed and dated an Institutional Review Board (IRB)/Independent Ethics Committee (IEC)-approved written informed consent form (ICF) in accordance with regulatory, local, and institutional guidelines. This must be obtained before the performance of any protocol-related procedures that are not part of normal patient care.

2) Type of Participant and Target Disease Characteristics

- a) Has adequate acoustic windows, to enable accurate TTEs as determined by the echocardiography core laboratory
- b) Men or women diagnosed with oHCM consistent with current American College of Cardiology Foundation/American Heart Association and European Society of Cardiology guidelines, satisfying both of the following criteria:
 - i) Has unexplained LV hypertrophy with nondilated ventricular chambers in the absence of other cardiac (eg, hypertension, aortic stenosis) or systemic disease and with maximal LV wall thickness ≥ 15 mm (or ≥ 13 mm with positive family history of hypertrophic cardiomyopathy or with a known disease-causing mutation), as determined by core laboratory interpretation
 - AND
 - ii) Has a LVOT peak gradient during screening as assessed by echocardiography of ≥ 50 mm Hg at rest, or ≥ 30 mm Hg at rest and ≥ 50 mm Hg with Valsalva maneuver (confirmed by echocardiography core laboratory interpretation)
- c) Has resting LVEF [REDACTED] at the Screening visit as determined by echocardiography core laboratory
- d) Has a valid measurement of LVOT post-exercise peak gradient at screening as determined by echocardiography core laboratory
- e) NYHA functional class II or III symptoms at screening
- f) A body weight of at least 45 kg and a body mass index (BMI) 18 to 37 kg/m², inclusive, at the Screening visit, calculated using the institution's standard formula.
- g) All safety laboratory parameters (chemistry, hematology, and urinalysis) within normal limits (laboratory reference range) at the Screening visit as assessed by the central laboratory, or if outside the limits must meet both of the following criteria:

- i) Considered by the investigator to be clinically insignificant
- ii) Alanine transaminase (ALT) or aspartate aminotransferase (AST) result must be $< 1.5 \times$ the upper limit of normal (ULN) of the laboratory reference range
- iii) The body size-adjusted estimated glomerular filtration rate is ≥ 30 mL/min/1.73 m², in the absence of dialysis
- h) Must be able to complete the KCCQ-23 per established guidelines

3) Age of Participant

Participant must be 18 to 80 years of age inclusive, or the local age of majority provided it is over 18 years of age, at the time of signing the informed consent.

4) Reproductive Status

- Investigators shall counsel women of childbearing potential (WOCBP), and male participants who are sexually active with WOCBP, on the importance of pregnancy prevention, the implications of an unexpected pregnancy, and the potential of fetal toxicity occurring due to transmission of study intervention, present in seminal fluid, to a developing fetus, even if the participant has undergone a successful vasectomy or if the partner is pregnant.
- The investigator shall evaluate the effectiveness of the contraceptive method in relationship to the first dose of study intervention.
- Local laws and regulations may require the use of alternative and/or additional contraception methods.

a) Female Participants:

- i) Female participants must have documented proof that they are not of childbearing potential.
- ii) Women who are not of childbearing potential are exempt from contraceptive requirements.
- iii) WOCBP must have a negative highly sensitive urine pregnancy test (minimum sensitivity 25 IU/L or equivalent units of human chorionic gonadotropin) within 24 hours prior to the start of study intervention.
- If a urine test cannot be confirmed as negative (eg, an ambiguous result), a serum pregnancy test is required. In such cases, the participant must be excluded from participation if the serum pregnancy result is positive.
- Additional requirements for pregnancy testing during and after study intervention are located in [Section 2](#), Schedule of Activities.
- The investigator is responsible for review of medical history, menstrual history, and recent sexual activity to decrease the risk for inclusion of a woman with an early undetected pregnancy.
 - iv) WOCBP must agree to follow instructions for method(s) of contraception defined in [Appendix 4](#) and as described below and included in the ICF.
- WOCBP are not permitted to use hormonal contraception methods alone as a highly effective method (as described in [Appendix 4](#)).
 - v) A female participant is eligible to participate if she is not pregnant or breastfeeding, and at least 1 of the following conditions applies:

(1) Is not a WOCBP

OR

(2) Is a WOCBP and using a contraceptive method that is highly effective (with a failure rate of < 1% per year), with low user dependency (User Independent), as described in [Appendix 4](#) during the intervention period and for at least 30 days after EOT and agrees not to donate eggs (ova, oocytes) for the purpose of reproduction for the same time period. The following methods are permitted (see Appendix 4):

(a) Intrauterine device (IUD) (eg, copper IUD)

(b) Intrauterine hormone-releasing system, in combination with a barrier method of birth control

(c) Bilateral tubal occlusion

(d) Vasectomized partner

(e) Sexual abstinence

b) Male Participants:

- i) Azoospermic males are not exempt from contraceptive requirements and will be required to always use a latex or other synthetic condom during any sexual activity (eg, vaginal, anal, oral) with WOCBP, even if the participant has undergone a successful vasectomy or if the partner is pregnant.
- ii) Male participants will be required to always use a latex or other synthetic condom during any sexual activity (eg, vaginal, anal, oral) with WOCBP, even if the participants have undergone a successful vasectomy or if their partner is already pregnant or breastfeeding. Males should continue to use a condom during the intervention period and for at least 30 days after the last dose of study intervention.
- iii) Female partners of males participating in the study should be advised to use highly effective methods of contraception during the intervention period and for at least 30 days after the last dose of study intervention in the male participant.
- iv) Male participants with a pregnant or breastfeeding partner must agree to remain abstinent from sexual activity or use a male condom during any sexual activity (eg, vaginal, anal, oral), even if the participants have undergone a successful vasectomy, during the intervention period and for at least 30 days after the last dose of study intervention.
- v) Male participants must refrain from donating sperm during the intervention period and for at least 30 days after the last dose of study intervention.
- vi) Breastfeeding partners should be advised to consult their health care providers about using appropriate highly effective contraception during the time the participant is required to use condoms.

PART B:

Participants that have successfully completed Part A of the study may enroll in Part B, an optional, 2-year open-label extension study. Eligibility for Part B will be assessed following completion of informed consent. Participants that have completed Part A EOS assessments within the Part B 28-day screening window may use those assessments for eligibility determination. Where possible,

participants should enroll in Part B of the study on the same background therapy on which they completed Part A.

5) Signed Written Informed Consent

A separate informed consent will be collected for participation in Part B. Participants must have signed and dated an Institutional Review Board (IRB)/Independent Ethics Committee (IEC)-approved written informed consent form (ICF) in accordance with regulatory, local, and institutional guidelines. This must be obtained before the performance of any protocol-related procedures that are not part of normal patient care.

6) Type of Participant and Target Disease Characteristics

- a) Must have successfully completed Part A through the EOS-A visit within 90 days of signing consent for Part B (participants who are beyond the 90-day window from the EOS-A visit may be included in this study pending Medical Monitor approval) and the investigator considers it to be in the participant's best interest to continue in the study.
- b) Has adequate acoustic windows, to enable accurate TTEs as determined by the echocardiography core laboratory
- c) Has documented resting LVEF [REDACTED] at the Screening visit as determined by local echocardiography
- d) A body weight of at least 45 kg and a BMI 18 to 37 kg/m², inclusive, at the Screening visit, calculated using the institution's standard formula.
- e) All safety laboratory parameters (chemistry, hematology, and urinalysis) within normal limits (laboratory reference range) at the Screening visit as assessed by the central laboratory, or if outside the limits must meet both of the following criteria:
 - vii) Considered by the investigator to be clinically insignificant
 - viii) ALT or AST result must be $< 1.5 \times$ the ULN of the laboratory reference range
 - ix) The body size-adjusted estimated glomerular filtration rate is ≥ 30 mL/min/1.73 m², in the absence of dialysis
- f) Must be able to complete the KCCQ-23 per established guidelines

7) Reproductive Status

- Investigators shall counsel women of childbearing potential (WOCBP), and male participants who are sexually active with WOCBP, on the importance of pregnancy prevention, the implications of an unexpected pregnancy, and the potential of fetal toxicity occurring due to transmission of study intervention, present in seminal fluid, to a developing fetus, even if the participant has undergone a successful vasectomy or if the partner is pregnant.
- The investigator shall evaluate the effectiveness of the contraceptive method in relationship to the first dose of study intervention.
- Local laws and regulations may require the use of alternative and/or additional contraception methods.
- Guidelines for both Female and Male participants outlined above in Part A ([Section 6.1](#), criterion 4) should be followed in Part B.

6.2 Exclusion Criteria

Participants are excluded from the study if any of the following criteria apply:

PART A:

1) Medical Conditions

- a) Presence of any medical condition that precludes exercise stress testing
- b) History of syncope or sustained ventricular tachyarrhythmia within 6 months prior to Screening
- c) Active infection
- d) Known infiltrative or storage disorder causing cardiac hypertrophy that mimics HCM, such as Fabry disease, amyloidosis, or Noonan syndrome with left ventricular hypertrophy
- e) Has been successfully treated with invasive septal reduction (surgical myectomy or percutaneous alcohol septal ablation [ASA]) within 6 months prior to Screening or plans to have either of these treatments during the study (Note: Individuals with an unsuccessful myectomy or percutaneous ASA procedure performed > 6 months prior to Screening may be enrolled if study eligibility criteria for LVOT gradient criteria are met).
- f) Implantable cardioverter-defibrillator (ICD) placement or pulse generator change within 2 months prior to screening or planned new ICD placement during the study (pulse generator changes, if needed during the study are allowed)
- g) Has a history of resuscitated sudden cardiac arrest (any time) or known history of appropriate implantable cardioverter-defibrillator (ICD) discharge for life-threatening ventricular arrhythmia within 6 months prior to screening
- h) Has paroxysmal atrial fibrillation with atrial fibrillation present per the Investigator's evaluation of the subject's ECG at the time of Screening
- i) Has persistent or permanent atrial fibrillation not on anticoagulation for at least 4 weeks prior to Screening and/or not adequately rate controlled within 6 months prior to Screening (Note: Participants with persistent or permanent atrial fibrillation who are anticoagulated and adequately rate-controlled are allowed. Please see restricted therapies in [Appendix 5](#)).
- j) Has QT interval with Fridericia correction (QTcF) > 500 msec when QRS interval < 120 msec or QTcF > 520 msec when QRS ≥ 120 msec if participant has left bundle branch block or any other 12-lead ECG abnormality considered by the investigator to pose a risk to participant safety (eg, second-degree atrioventricular block type II)
- k) Has known moderate or severe (per investigator's judgment) aortic valve stenosis at screening
- l) History of LV systolic dysfunction (LVEF < 45%) at any time during their clinical course
- m) Clinically significant pulmonary disease associated with exertional dyspnea
- n) Has known significant unrevascularized obstructive coronary artery disease (> 70% stenosis in one or more main epicardial coronary arteries) or history of myocardial infarction

Note: participants with prior coronary artery bypass grafting (CABG) or percutaneous coronary interventions (PCIs) are allowed if the procedure was performed at least 12 weeks prior to Screening.

- o) Positive serologic test at screening for infection with human immunodeficiency virus (HIV); hepatitis C virus (HCV); or hepatitis B virus (HBV), with the exception of hepatitis B s-antibody positive, which is a marker of immunity.
- p) Known active infection with COVID-19 (polymerase chain reaction [PCR] +). If subject had a PCR+ test at screening, they must be symptom free for 14 days and have a negative antibody test prior to dosing.
- q) **Not Applicable per Protocol Amendment 01:** History of malignancy of any type, with the following exceptions: in situ cervical cancer more than 5 years prior to Screening or surgically excised non-melanomatous skin cancers more than 2 years prior to Screening
- r) Has a history or evidence of any other clinically significant disorder, condition, or disease that, in the opinion of the investigator, would pose a risk to participant safety or interfere with the study evaluation, procedures, or completion
- s) Moderate to severe regurgitant or obstructive valvular heart disease in need of repair or other intracardiac procedure (or that may require it during study participation) or that may undermine the interpretation of clinical study data
- t) Acute heart failure from 4 weeks prior to Screening up to study Day 1A
- u) Heart transplant recipient or listed for heart transplant
- v) Currently implanted with LV assist device
- w) Any active or suspected malignancy or history of malignancy within 10 years of screening, except appropriately treated basal cell and non-metastatic squamous cell carcinoma of the skin, in situ carcinoma of the uterine cervix, or low risk prostate cancer (participants with pretreatment prostate-specific antigen of < 10 ng/mL, and biopsy Gleason score of ≤ 6 and clinical stage T1c or T2a)

2) Reproductive Status

- a) Women who are pregnant or breastfeeding

3) Prior/Concomitant Therapy

- a) Prior treatment with mavacamten or aficamten. An exception may be made in cases where myosin inhibitor use was not within 4 months of the Screening visit, and with the agreement of both the Investigator and the Medical Monitor.
- b) Prior treatment with cardiotoxic agents such as anthracyclines (eg, doxorubicin) or similar

c)

d)

- e) Prior therapy with MYK-224. An exception is made for participants that have not received a dose of MYK-224 within 30 days of the Screening visit and with the agreement of both the investigator and the Medical Monitor.

f) Cohort 1:

- i) The following are excluded:

- (1) For individuals on beta-blockers, any dose adjustment of that medication < 14 days prior to screening or an anticipated change in regimen during the study
- (2) Current (within 14 days prior to screening) or planned treatment during the study with nondihydropyridine calcium channel-blockers, disopyramide, cibenzoline, or ranolazine. Participants on any of these medications who, in the opinion of the investigator, can be safely withdrawn are eligible as long as medication is discontinued at least 14 days prior to the Screening visit.

g) Cohort 2:

i) The following are excluded:

- (1) For individuals on verapamil, diltiazem, or disopyramide any dose adjustment of that medication < 14 days prior to screening or an anticipated change in regimen during the study
- (2) Current treatment (within 14 days prior to screening) or planned treatment during the study with a combination of beta-blockers and verapamil, or a combination of beta-blockers and diltiazem or beta-blockers alone
- (3) Current treatment (within 14 days prior to screening) or planned treatment during the study with cibenzoline or ranolazine

4) Physical and Laboratory Test Findings

- a) Evidence of organ dysfunction or any clinically significant deviation from normal in physical examination, vital signs, ECG, or clinical laboratory determinations beyond what is consistent with the target population

5) Allergies and Adverse Drug Reaction

- a) Hypersensitivity to MYK-224 or any of the components of the MYK-224 formulation, [REDACTED]
- b) History of significant adhesive allergy that would preclude the use of the cardiac monitor and patch
- c) History of any significant allergy (such as anaphylaxis or hepatotoxicity) to any food, drug, or other substance

6) Other Exclusion Criteria

- a) Prisoners or participants who are involuntarily incarcerated.
- b) Unable to comply with the study restrictions/requirements, including the number of required visits to the clinic site
- c) Planned invasive procedure during the study period
- d) Current or recent (within 3 months of study intervention administration) gastrointestinal disease that could impact upon the absorption of study intervention
- e) Any major surgery within 4 weeks of study intervention administration
- f) Any gastrointestinal surgery that could impact upon the absorption of study intervention
- g) Donation of blood to a blood bank or in a clinical study (except at screening visit) within 4 weeks of study intervention administration (within 2 weeks for plasma only). Blood draws for routine medical purposes are acceptable.
- h) Blood transfusion within 4 weeks of study intervention administration
- i) Inability to tolerate oral medication

- j) Inability to be venipunctured and/or tolerate venous access
- k) Participated in a clinical trial where the participant received any investigational drug (or is currently using an investigational device) within 30 days prior to Screening, or at least 5 times the respective elimination half-life (whichever is longer)
- l) Recent (within 6 months of study intervention administration) drug or alcohol abuse as defined in DSM 5, Diagnostic Criteria for Drug and Alcohol Abuse
- m) Is employed by, or is a relative of, someone employed by the Sponsor or the investigator
- n) Any other sound medical, psychiatric, and/or social reason as determined by the investigator

PART B:

7) Medical Conditions

- a) Presence of any medical condition that precludes exercise stress testing
- b) Interval history of syncope or sustained ventricular tachyarrhythmia between the Part A EOS visit and the Part B Screening visit for participants that have a separate Screening visit for Part B
- c) Active infection
- d) Has been treated with invasive septal reduction (surgical myectomy or percutaneous alcohol septal ablation [ASA]) following enrollment in Part A
- e) Has an interval history of resuscitated sudden cardiac arrest or of appropriate implantable cardioverter-defibrillator (ICD) discharge for life-threatening ventricular arrhythmia between Part A EOS visit and Screening for Part B
- f) Has paroxysmal, intermittent atrial fibrillation with atrial fibrillation present per the Investigator's evaluation of the subject's ECG at the time of Screening for Part B
- g) Has persistent or permanent atrial fibrillation not on anticoagulation for at least 4 weeks prior to Screening for Part B and/or not adequately rate controlled (Note: Participants with persistent or permanent atrial fibrillation who are anticoagulated and adequately rate-controlled are allowed. Please see restricted therapies in [Appendix 5](#)).
- h) Heart transplant or listed for heart transplant following enrollment in Part A
- i) Currently implanted LV assist device
- j) Clinically significant pulmonary disease associated with exertional dyspnea
- k) Has known significant unrevascularized obstructive coronary artery disease (> 70% stenosis in one or more epicardial coronary arteries) or history of myocardial infarction since enrollment in Part A

Note: participants with prior coronary artery bypass grafting (CABG) or percutaneous coronary interventions (PCIs) are allowed if the procedure was performed at least 12 weeks prior to Screening
- l) Has QT interval with Fridericia correction (QTcF) > 500 msec when QRS interval < 120 msec or QTcF > 520 msec when QRS ≥ 120 msec or any other 12-lead ECG abnormality considered by the investigator to pose a risk to participant safety (eg, second-degree atrioventricular block type II) at Screening for Part B

- m) Has known moderate or severe (per investigator's judgment) aortic valve stenosis at Screening for Part B
- n) Positive serologic test at the Part B screening visit for infection with human immunodeficiency virus (HIV); hepatitis C virus (HCV); or hepatitis B virus (HBV), with the exception of hepatitis B s-antibody positive, which is a marker of immunity
- o) Known active infection with COVID-19 (polymerase chain reaction [PCR]+). If subject had a PCR+ test, they must be symptom free for 14 days prior to dosing
- p) Interval development of significant malignant disease since enrollment in Part A, except appropriately treated basal cell and non-metastatic squamous cell carcinoma of the skin, in situ carcinoma of the uterine cervix, or low risk prostate cancer (participants with pretreatment prostate-specific antigen of < 10 ng/mL, and biopsy Gleason score of ≤ 6 and clinical stage T1c or T2a)
- q) Has a history or evidence of any other clinically significant disorder, condition, or disease that, in the opinion of the investigator, would pose a risk to participant safety or interfere with the study evaluation, procedures, or completion

8) Reproductive Status

- a) Women who are pregnant or breastfeeding

9) Prior/Concomitant Therapy

- a) Interval treatment with mavacamten or aficamten between Part A EOS Visit and Screening for Part B
- b) Prior treatment with cardiotoxic agents such as anthracyclines (eg, doxorubicin) or similar
- c) 
- d) 

10) Physical and Laboratory Test Findings

- a) Evidence of organ dysfunction or any clinically significant deviation from normal in physical examination, vital signs, ECG, or clinical laboratory determinations beyond what is consistent with the target population

11) Allergies and Adverse Drug Reaction

- a) Hypersensitivity to MYK-224 or any of the components of the MYK-224 formulation, [REDACTED]
- b) Development any significant allergy (such as anaphylaxis or hepatotoxicity) to any food, drug, or other substance since participation in Part A

12) Other Exclusion Criteria

- a) Prisoners or participants who are involuntarily incarcerated.
- b) Unable to comply with the study restrictions/requirements, including the number of required visits to the clinic site
- c) Planned invasive procedure during the study period
- d) Current or recent (within 3 months of study intervention administration) gastrointestinal disease that could impact upon the absorption of study intervention
- e) Any major surgery within 4 weeks of study intervention administration
- f) Any gastrointestinal surgery that could impact upon the absorption of study intervention
- g) Blood transfusion within 4 weeks of study intervention administration
- h) Inability to tolerate oral medication
- i) Inability to be venipunctured and/or tolerate venous access
- j) Participated in a clinical trial where the participant received any investigational drug, other than MYK-224, (or is currently using an investigational device) within 30 days prior to Screening for Part B, or at least 5 times the respective elimination half-life (whichever is longer).
- k) Recent (within 6 months of study intervention administration) drug or alcohol abuse as defined in DSM 5, Diagnostic Criteria for Drug and Alcohol Abuse
- l) Is employed by, or is a relative of, someone employed by the Sponsor or the investigator
- m) Any other sound medical, psychiatric, and/or social reason as determined by the investigator

Eligibility criteria for this study have been carefully considered to ensure the safety of the study participants and that the results of the study can be used. It is imperative that participants fully meet all eligibility criteria.

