8.1.1.1 Echocardiographic Temporary Discontinuation Criteria

8.1.1.2 12-Lead ECG Temporary Discontinuation Criteria

Criteria for temporary discontinuation due to QTcF prolongation are as follows and depend on QRS width as determined by local ECG:

- If QRS is narrow (< 120 ms), QTcF ≥ 520 ms
- If QRS is wide (≥ 120 ms), QTcF ≥ 550 ms

If QTcF performed at the first follow-up visit persists as out of range, at the second follow-up visit, study drug will be discontinued permanently.

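### Part A exclusion 1) j) sets no numeric QTcF entry limit for a wide QRS without left bundle branch block, unlike Part B 7) l) and the interruption rule in Section 8.1.1.2

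*Combined protocol and SAP*

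**What the plan says.** Three places in the protocol set QTcF limits by QRS width.

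- **Section 6.2, Part A, 1) j).** The narrow-QRS limb reads "Has QT interval with Fridericia correction (QTcF) > 500 msec when QRS interval < 120 msec". The wide-QRS limb reads "QTcF > 520 msec when QRS ≥ 120 msec if participant has left bundle branch block or any other 12-lead ECG abnormality", and the sentence goes on "considered by the investigator to pose a risk to participant safety (eg, second-degree atrioventricular block type II".
- **Section 6.2, Part B, 7) l).** The narrow-QRS limb has the same numbers. The wide-QRS limb reads "QTcF > 520 msec when QRS ≥ 120 msec or any other 12-lead ECG abnormality considered by the investigator", with no bundle-branch condition.
- **Section 8.1.1.2.** The criteria for temporary discontinuation "depend on QRS width as determined by local ECG". They are "If QRS is narrow (< 120 ms), QTcF ≥ 520 ms" and "If QRS is wide (≥ 120 ms), QTcF ≥ 550 ms". Persistence has a further consequence: "If QTcF performed at the first follow-up visit persists as out of range, at the second follow-up visit, study drug will be discontinued permanently".

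Two other Part A exclusions bear on the ECG without giving a QTcF value. Exclusion 1) r) covers other clinically significant conditions that the investigator considers a risk. Exclusion 4) a) covers clinically significant departures from normal, ECG included, beyond what fits the target population.

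**The concern.** Of the three rules, only the Part A one depends on why the QRS is wide, and nothing in the protocol explains the difference. Sections 6 and 9 rule out waivers, and Section 6.2 closes by insisting that every criterion be fully met, so sites have to apply the sentence as it stands.

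Taken literally, the sentence lets a site dose someone in Part A whose QTcF is already at the level at which Section 8.1.1.2 tells the site to interrupt. ECGs are taken before and after the first dose on Day 1A (Table 2-1), so the conflict could surface at once. Safety is the primary objective of this single-arm study, and Section 10.4.2 plans a categorical analysis of post-dose QTcF by subgroup. A value that was long before dosing could appear there with no control arm to set it against. Because the remaining safeguard is judgement, sites may also admit different participants.

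**Working it through.** No sample size, power or error rate is involved, so the check is a comparison of limits. The inputs are the three rules listed above. The gap is the Section 8.1.1.2 threshold minus the Part A entry limit.

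| Group | Part A 1) j) excludes | Part B 7) l) excludes | Section 8.1.1.2 interrupts | Gap in Part A |
|---|---|---|---|---|
| QRS < 120 ms | QTcF > 500 | QTcF > 500 | QTcF ≥ 520 | 520 − 500 = 20 ms |
| QRS ≥ 120 ms, LBBB | QTcF > 520 | QTcF > 520 | QTcF ≥ 550 | 550 − 520 = 30 ms |
| QRS ≥ 120 ms, no LBBB | no number given | QTcF > 520 | QTcF ≥ 550 | none: no entry limit to subtract |

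In Part B the gaps are 20 ms for narrow and 30 ms for every wide QRS, so no group is left open.

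Within the third row, two ranges behave differently.

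- **QTcF above 520 and below 550 ms:** not numerically excluded from Part A, excluded from Part B, and below the interruption threshold.
- **QTcF 550 ms or more:** not numerically excluded from Part A, excluded from Part B, and already at the interruption threshold.

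Worked case: QRS 140 ms, no LBBB, QTcF 555 ms. The Part A narrow limb does not apply (140 ≥ 120), and the wide limb does not apply (no LBBB). Part B excludes (555 > 520). Section 8.1.1.2 is met (555 ≥ 550).

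The Part A sentence can be parsed in more than one way, so each reading was tried.

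1. *The LBBB condition attaches to the wide limb, and the other abnormality is a separate exclusion.* The third row is open. Part B's wording supports treating the other abnormality as separate.
2. *The condition is LBBB or another abnormality judged a risk.* A wide QRS of another cause that is not judged a risk still has no limit. Under this reading the second-degree AV block named as an example would exclude only together with QRS ≥ 120 ms and QTcF > 520 ms, which Part B's wording does not allow.
3. *The condition governs both QTcF limbs.* The third row is still open.
4. *LBBB merely illustrates a wide QRS.* This closes the gap, but the text states a condition. The same sentence marks its AV-block example explicitly as an example and does not do so for LBBB.

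Three of the four readings leave the group without a numeric limit. The fourth departs from the wording.

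**The case against.** The strongest reply is that such a participant is not unprotected. The end of 1) j), together with 1) r) and 4) a), lets the investigator exclude on judgement. Eligibility is reviewed again on Day 1, when a pre-dose ECG is taken (Table 2-1). For the worked case to be dosed, a QTcF of 555 ms would have to be accepted at Screening and again on Day 1. This stands: a reader might infer that Part A has no QTcF safeguard at all for this group, and that would be wrong. What is missing is a number. None of the three judgement clauses names a QTcF value or requires exclusion at one.

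The reply also limits the consequences.

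- **Loss of an evaluable participant.** A reader might infer this, but it does not follow. The stop in Section 8.1.1.2 is temporary at first and becomes permanent only on persistence. The Efficacy/PD set (Section 10.3) needs one dose, a baseline and one post-baseline value. Section 8.1.3 asks those who stop permanently to attend an end-of-treatment visit and remain for washout and end of study.
- **A false drug signal.** This too is only partly supported. Section 10.4.2 gives no categories for the QTcF analysis. It also plans changes from baseline, with baseline the last pre-dose value (Section 10.4.1), which would show that the prolongation came first. The categorical analysis, as described, would not show this.
- **Frequency.** The protocol admits participants with ICDs and some with earlier unsuccessful septal reduction, but says nothing about how many have a wide QRS without LBBB. The group may be very small.

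**Conclusion.** The point holds as an inconsistency between parallel criteria that leaves one group without a stated threshold. Part A gives no numeric QTcF entry limit for QRS ≥ 120 ms without LBBB. Part B sets 520 ms for the same people, and Section 8.1.1.2 interrupts at 550 ms whatever the cause of the wide QRS. The role of the investigator-judged abnormality in the Part A sentence is also ambiguous.

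The size can be stated only as the missing margin, against 20 and 30 ms in the other two groups. The number of participants affected cannot be estimated from the documents. The conclusion assumes that sites apply the sentence literally and that the blacked-out text holds no further QTcF limit.

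A reader might infer that the LBBB clause is a slip and that Part B carries the correct rule. The documents do not establish that: the restriction could be deliberate, and the choice is a clinical one. They show only that the three passages do not fit together. Since this is an eligibility threshold bearing on the primary safety objective, it is worth correcting even if few people are concerned.

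**What to change.** Reconcile Part A 1) j) with Part B 7) l) and Section 8.1.1.2, so that the protocol answers two questions:

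1. Which QTcF entry criterion, if any, applies in Part A when QRS is 120 ms or more and LBBB is absent? If the difference from Part B is intended, give the reason and say how a participant already at the Section 8.1.1.2 threshold before dosing is to be handled.
2. Is the investigator-judged ECG abnormality an exclusion in its own right, or a condition on the QTcF limit? Setting it as a separate sub-item or rewording the sentence would settle this either way.

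The sponsor, with its clinical advisers, decides which rule is intended. The cost is one clause in an amendment and a note to sites. If the outcome is a numeric limit for this group, a few more people may be excluded at screening.
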